5.2.5. Electrocardiograms

Electrocardiogram (ECG) parameters include heart rate, PR interval, RR interval, and QT, QTcB, QTcF and QRS intervals. Change from baseline to each post-baseline visit will be calculated and summarized by visit as collected and not windowed. Visits and timepoints only collected for PK subjects will be listed but not summarized.

Collected QTcB and QTcF will not be used, but will instead be derived from the QT and RR (converted from collected msec to sec) interval based on the following formulas:

$$QTcB = \frac{QT}{\sqrt{RR}}$$

$$QTcF = \frac{QT}{\sqrt[3]{RR}}$$

If QT and/or RR is missing, the QTcB and QTcF will be left as missing.

Potentially clinically significant ECG findings will be identified using the criteria which are included in Table 16. ECG results are interpreted as clinically significant or not clinically significant.

Table 16 Potentially Clinically Significant Criteria for ECG

ECG Parameter	Criterion value
Heart Rate	>120 bpm
	<50 bpm
PR Interval	≥ 210ms
RR Interval	> 1200ms
	< 500ms
QRS Interval	≥ 120ms
	≤ 50ms
QT Interval	≥ 500ms
	≤ 300ms
QTcB, QTcF Intervals	≥ 500ms
	≥ 480ms
	≥ 450ms
	≤ 300ms
	Change from baseline ≥ 30 ms
	Change from baseline ≥ 60 ms

5.2.6. Physical Examination

Physical examination is conducted during screening, on Day 1 of each cycle, and at the post-treatment visit. Abnormal findings in PE were to be reported as AEs. These data will not be summarized, i.e. they will only be available in listings.

6. ANALYSIS METHODS

6.1. General Principles of Analysis

6.1.1. General Methodology

In general, all efficacy, safety and PK variables will be summarized using descriptive statistics and graphs as appropriate. Continuous variables will be summarized by descriptive statistics (sample size (n), mean, standard deviation, minimum, median, and maximum). Categorical variables will be summarized in frequency tables (frequencies and percentages).

Survival estimates will be analyzed with Kaplan-Meier method and summarized with median, twenty-fifth and seventy-fifth percentiles, and 95% confidence intervals (CI), if applicable. Individual data will be presented in patient listings.

Analyses will be implemented using SAS[®] 9.4 or higher (SAS Institute, Cary, North Carolina, USA). The International Conference on Harmonization (ICH) numbering convention, i.e. ICH-E3, will be used for all tables and listings. Upon completion, all SAS[®] programs will be validated by an independent programmer within the staff of the third-party vendor doing the primary analysis. The validation process will be used to confirm that statistically valid methods have been implemented and that all data transformations and calculations are accurate. Checks will be made to ensure accuracy, consistency with this plan, consistency within tables, and consistency between tables and corresponding data listings.

All summary tables, listings, and figures (TLFs) will be presented by treatment groups as defined in [Table 17](#).

Table 17 Treatment Display in TLFs

Treatment Group	Treatment Description in Data Display
1	Placebo + E/P/A
2	Trilaciclib 240 mg/m ² + E/P/A

All statistical tests will be presented at a two-sided .05 alpha level unless otherwise specified. The primary comparison will be conducted between placebo group and Trilaciclib group. Where appropriate, model-based point estimates, together with their 95% CIs will be presented along with the two-sided p-values for the tests. P-value will be presented to 4 decimal places, if the p-value <0.0001, the value will be presented as “<0.0001”.

For continuous data, the same number of decimal places as in the raw data will be presented when reporting mean, median, minimum and maximum; one more decimal place than in the raw data will be presented when reporting standard deviation and standard error (SE). The derived variables will be presented with 1 decimal place. Percentages will be reported with 1 decimal point; if the count is 0, no percentage will be presented. Value of percentage less than 1% will be presented as “<1%.” Value of percentage less than 100% but ≥ 99.5% will be presented as “>99%.” Any rounding will be done after all calculations are made.

6.1.2. Handling of Missing Data

In general, the observed case (OC) data for a visit will consist of the actual observations recorded for the visit. If missing, the OC data will remain missing — no missing imputation will be performed. Safety analyses will be conducted on the OC data only. However, imputation of

missing AE and concomitant medication onset and stop dates will be used to determine the status of each AE and the prior/concomitant status of each medication. Please refer to [Section 5.2.2](#) for the method of imputation of missing AE onset and stop date and [Section 6.2.5](#) for the method of imputation of missing concomitant onset and stop dates.

For demographic and baseline characteristics, each variable will be analyzed and/or summarized using the available data. Patients with missing data will be excluded only from analyses for which data are not available.

For the efficacy analyses, missing data will be excluded except for the sensitivity analyses noted in [Section 6.2.7.1.5](#).

6.1.3. Visit Windowing

It is expected that there will be a variation between patients in the actual number of study days from the start of administration of study drug within each cycle – defined as Day 1 – to the dates that the scheduled visits occur. To handle this, for tables and figures where data are grouped by visit, assessments will be categorized using visit windows based on study days (relative to the Day 1 of each cycle). The visit-window mapping is described in [Table 18](#). Visit-based summaries will be based on the windowed visits. All data, whether or not within the visit windows, will be presented in patient listings.

For windowed visits during the treatment cycles, if more than 1 visit occurs during a visit window, the visit closest to the scheduled day will be assigned to the windowed visit. If two visits are equidistant from the scheduled day, the later visit will be assigned to the windowed visit. If there are multiple assessments on the same day, the worst case will be used. For the assigned follow-up visit, the last assessment in the window will be included in the summary.

Only induction treatment cycles will have windowed visits. For maintenance treatment cycles, nominal visits will be used as all assessments are scheduled for Day 1 of each cycle.

Table 18 Visit Windowing

Visit	Induction Cycles					Post-treatment [d]	Post-Treatment Visit + 60 days [e]
	C1D1	C1D3	C1D8	C1D15	EOC		
Scheduled Day [a]	1	3[e]	8	15	22		
Clinical Chemistry [b]	Day -3 to 1				2 to EOC	From first dose date of last cycle to first dose date of last cycle + 30	Relative to the first dose date of last cycle, the last assessment falling the window between 31 and 89.
Hematology [c]	Day -1 to 1	1 to 5	6 to 11	12 to 18	19 to EOC	From first dose date of last cycle to first dose date of last cycle + 30	Relative to the first dose date of last cycle, the last assessment falling the window between 31 and 89.

[a] The scheduled day is relative to the Day 1 of each cycle.

[b] Clinical chemistry may be obtained up to 72 hours prior to the first dose of each cycle.

[c] Hematology may be obtained up to 24 hours prior to dosing on Days 1 and 3 of each cycle, Days 8 and 15 of each cycle, at the Post-Treatment Visit, and at 60 days after the Post-Treatment Visit.

[d] 30 ± 3 days after the last dose of study drug. Only windowing for subjects that have completed treatment.

[e] 60 ± 7 days after the post-treatment visit. Only windowing for subjects that have completed treatment

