c Patients will return to the study center for post-treatment visits at 30 (+3) and 90 (+7) days after the last dose of study drug.

d Monthly phone calls will be made to each patient that is in the Survival Follow-up Phase. Patients will be followed for survival until at least 70% of the patients have died. Any anticancer therapies used will be collected.

e Informed consent may be obtained up to 28 days prior to the first study treatment administration.

f Including medical, surgical, radiation history, smoking history, family history, documentation of tumor diagnosis, baseline signs and symptoms within 4 weeks prior to randomization, weight loss in the 6 months prior to randomization (≤ 5% or > 5%), and medications taken within 14 days of enrollment.

g Height will only be measured at the screening visit. Weight will only be measured at the screening visit and on Day 1 of each cycle. Body surface area calculation (based on actual body weight) will be completed on Day 1 of each cycle and vital signs obtained within 15 minutes before and after trilaciclib or placebo and E/P/A infusions. Vitals only need to be taken before the trilaciclib or placebo infusion, between each subsequent infusion, and after the last infusion on Days 1 and 3.

h Clinical chemistry (albumin, alkaline phosphatase, total bilirubin, calcium, chloride, creatinine, glucose, inorganic phosphorus, potassium, total protein, ALT, AST, lactate dehydrogenase [LDH], sodium, and blood urea nitrogen [BUN], amylase, lipase) and urine analysis may be obtained up to 72 hours prior to the first dose of each cycle of trilaciclib or placebo + E/P/A therapy (induction part) or atezolizumab (maintenance part).

i Hematology will be obtained (hemoglobin, white blood cells (WBC) with differential, and platelet counts). Hematology may be obtained up to 24 hours prior to first dose of each cycle of trilaciclib/placebo + E/P/A therapy (induction part) or atezolizumab (maintenance part).

j For female patients of childbearing potential: serum β-hCG at enrollment; and serum or urine β-hCG obtained at the post-treatment visits.

k Randomization is to be done within 3 days prior to first dose of trilaciclib or placebo + E/P/A therapy, following confirmation that the patient is eligible for the study.

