5.1.3.5. ANC, Platelet Count, Absolute Lymphocyte Counts (ALC), and Hemoglobin Change over Time

For the hematologic parameters consisting of ANC, hemoglobin, platelet count, and ALC, the observed lab values in each windowed visit as detailed in [Section 6.1.3](#) will be appropriately identified for further analysis.

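### SAP Table 18 puts Day 1 in both the Day 1 and the Day 3 hematology windows, so under specific conditions a pre-dose count is reported as the Day 3 value

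*SAP*

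**What the plan says.** SAP Section 6.1.3 maps assessments to visits by study day within each cycle and states that "Visit-based summaries will be based on the windowed visits". In Table 18 the Hematology row reads, across the five induction columns (Days 1, 3, 8, 15 and end of cycle), "Day -1 to 1 1 to 5 6 to 11 12 to 18 19 to EOC". Day 1 therefore closes the first window and opens the second.

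When a window holds several samples, "if more than 1 visit occurs during a visit window, the visit closest to the scheduled day will be assigned to the windowed visit". For ties, "If two visits are equidistant from the scheduled day, the later visit will be assigned to the windowed visit". No sentence confines a sample to one window, and none separates pre-dose from post-dose samples on Day 1.

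Three other places bear on the point:

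- The Day 1 count is pre-dose. Protocol Section 10.3.1 has it obtained and reviewed before dosing, and footnote i of the SAP's schedule of assessments (Table 2) adds: "Hematology may be obtained up to 24 hours prior to first dose of each cycle".
- SAP Section 6.1.2 says of observed-case visit data: "If missing, the OC data will remain missing — no missing imputation will be performed".
- SAP Section 5.1.3.5 bases the analyses of ANC, hemoglobin, platelets and lymphocytes over time on "the observed lab values in each windowed visit as detailed in" Section 6.1.3.

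**The concern.** The Day 3 visit comes after two days of chemotherapy; the Day 1 sample comes before any in that cycle. If one sample can fill both visits, a missed Day 3 draw appears in the tables as an observed Day 3 value rather than as missing. The Day 3 summary then mixes pre-dose and post-dose counts, and the number of patients with a Day 3 value is overstated.

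The outputs at stake are the counts over time, a supportive secondary endpoint in protocol Table 5-1, and the by-visit laboratory tables of SAP Section 6.2.8.3. The overlap looks like a drafting slip. Within a cycle, every other hematology boundary is disjoint (5/6, 11/12, 18/19), and the chemistry row also separates cleanly (up to Day 1, then from Day 2).

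**Working it through.** The plan states no figure here to reproduce. The check applies the written rules to patterns of sampling days.

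**Inputs.** Windows from Table 18: Day 1 visit, -1 to 1; Day 3, 1 to 5; Day 8, 6 to 11; Day 15, 12 to 18. Scheduled induction hematology on Days 1, 3, 8 and 15 (protocol Table 9-1, SAP Table 2).

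**Rule.** A sample on day d is a candidate for a window from a to b, with scheduled day s, if a ≤ d ≤ b. With several candidates, take the smallest |d − s|; if tied, the later day.

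**Results for the Day 3 visit (s = 3).**

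| Sampling days | Candidates, window 1 to 5 | Day 3 value as written | Day 3 value, window 2 to 5 |
|---|---|---|---|
| 1, 3, 8, 15 | Day 1 (distance 2), Day 3 (distance 0) | Day 3 | Day 3 |
| 1, 8, 15 | Day 1 only | **Day 1, pre-dose** | missing |
| 1, 6, 15 | Day 1 only | **Day 1, pre-dose** | missing |
| 1, 2, 8, 15 | Day 1 (2), Day 2 (1) | Day 2 | Day 2 |
| 1, 4, 8, 15 | Day 1 (2), Day 4 (1) | Day 4 | Day 4 |
| 1, 5, 8, 15 | Day 1 (2), Day 5 (2), tied | Day 5 | Day 5 |
| -1, 8, 15 | none | missing | missing |

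So the substitution needs three things together: no Day 3 sample, a pre-dose sample drawn on Day 1 rather than the day before, and no sample on Day 2, 4 or 5. As an invented example, take an ANC of 4.0 on Day 1 pre-dose, no Day 3 draw, and 0.9 on Day 8. The reported Day 3 ANC is 4.0 instead of missing.

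**Coverage.** As written, Day 1 is the only day from -1 to 18 that falls in two windows. With the Day 3 window at 2 to 5, none falls in two and none is left out.

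**Change from baseline.** SAP Section 5 defines study baseline B as the last value before study drug. In Cycle 1 a pre-dose Day 1 sample is B itself, so the reported Day 3 change is B − B = 0. In Cycles 2 to 4, with pre-dose count D for that cycle, the reported change is D − B, which is generally not zero.

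**Reach.**

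- Affected: windowed values over time and their plots (Sections 5.1.3.5 and 6.2.7.2.4), and observed values, changes and CTCAE grades by visit (Section 6.2.8.3).
- Not affected: occurrence and duration of severe neutropenia (Section 5.1.1), which use actual assessment dates; cycle nadir (Section 5), the lowest value in the cycle; Grade 3 and 4 hematologic toxicity (Section 5.1.3.3), counted per cycle from any value; and worst-grade shifts (Section 6.2.8.3), which use scheduled and unscheduled data. Counts over time are not among the five hypotheses in Section 6.2.7.1.4.

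**The case against.** The best defence is that a sensible programmer would not do this. A sample taken on scheduled Day 1 is naturally a Day 1 visit, nothing says that one sample may fill two visits, and Section 6.1.2 leaves missing visits missing. Read together, the two sections suggest that Day 3 should stay empty. That is very likely the intention, and it is why this is a correction to one cell rather than a dispute about method. But the intention is not written down. Section 6.1.1 has programs validated for consistency with the plan, and literal application of Table 18 gives the wrong value. Two programmers could also resolve the overlap differently.

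It is also fair to say that the closest-visit rule is not what goes wrong. In the affected patterns it never operates, because only one sample is in the window. The fault is in the table row.

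A reader might infer more than the documents support:

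- *That every missed Day 3 draw becomes a false absence of change.* The table above shows otherwise, and outside Cycle 1 the change from study baseline is not zero in general.
- *That the Day 3 change shrinks by a factor (1 − m), where m is the missing fraction.* For m = 0.05, 0.10 and 0.20 this gives 5%, 10% and 20%, but those figures only restate an assumed m. The formula also requires that missed draws be unrelated to the count and that every affected patient was sampled on Day 1 itself. Beyond Cycle 1 it describes a change from cycle baseline, which the SAP does not list as a Day 3 summary.
- *That Day 3 looks better than it was, and more so in one arm.* The documents give no Day 3 counts and no missing rates by arm. The cycle-start criteria (ANC at least 1.5 × 10⁹/L, platelets at least 100 × 10⁹/L) say nothing about hemoglobin or lymphocytes.

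**Conclusion.** The overlap is real and the rule is wrong as written: under the three stated conditions a pre-dose count is reported as a Day 3 value, against the SAP's own missing-data principle. The conclusion rests on reading Table 18 literally, with no unwritten rule that a sample is used once.

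The consequence is small. It is confined to descriptive Day 3 hematology output, and no tested hypothesis depends on it. Its size and direction cannot be determined from the documents. Day 3 is a scheduled dosing visit, so missed draws may be few, but that too is an assumption.

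**What to change.** In Table 18, change the Day 3 hematology window from 1 to 5 to 2 to 5. Add a sentence to Section 6.1.3 stating that, within a cycle, pre-dose samples are assigned only to that cycle's Day 1 visit. The words *within a cycle* matter: Section 5 defines the end of a cycle as Day 1 of the next, and the sentence should not alter what the preceding cycle's end-of-cycle window may use.

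The shorter window still allows for footnote [c] of Table 18, since 24 hours before Day 3 dosing reaches back only to Day 2. No result changes where a Day 2, 3, 4 or 5 sample exists. The cost is one table cell and one sentence, with no change to data collection, design or the primary analysis.

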Survival Follow-up d																		X

AE = adverse event; Eval. = evaluation; [REDACTED]; irRECIST = immune-related RECIST; [REDACTED]; PK = pharmacokinetics; RECIST v1.1 = Response Evaluation Criteria in Solid Tumors, Version 1.1; T3 = tri-iodothyronine; T4 = thyroxine; TSH = thyroid-stimulating hormone

- a During the induction part, study drug administration (trilaciclib or placebo plus E/P/A) will continue for up to four 21-day cycles or until disease progression per RECIST v1.1, unacceptable toxicity, withdrawal of consent, or discontinuation by investigator, whichever occurs first. Following disease progression per RECIST v1.1, if the patient appears to be deriving clinical benefit, the investigator believes it is in the best interest of the patient, and the patient has provided re-consent, study drug administration may be continued until loss of clinical benefit.
- b During the maintenance part, study drug administration (atezolizumab) will continue in 21-day cycles until disease progression per RECIST v1.1, unacceptable toxicity, withdrawal of consent, or discontinuation by investigator, whichever occurs first. Following disease progression per RECIST v1.1, if the patient appears to be deriving clinical benefit, the investigator believes it is in the best interest of the patient, and the patient has provided re-consent, study drug administration may be continued until loss of clinical benefit.
- c Patients will return to the study center for post-treatment visits at 30 (+3) and 90 (+7) days after the last dose of study drug.
- d Monthly phone calls will be made to each patient that is in the Survival Follow-up Phase. Patients will be followed for survival until at least 70% of the patients have died. Any anticancer therapies used will be collected.
- e Informed consent may be obtained up to 28 days prior to the first study treatment administration.
- f Including medical, surgical, radiation history, smoking history, family history, documentation of tumor diagnosis, baseline signs and symptoms within 4 weeks prior to randomization, weight loss in the 6 months prior to randomization ( $\leq 5\%$  or  $> 5\%$ ), and medications taken within 14 days of enrollment.

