#### **10.6. Post-Treatment Visits**

Patients will return to the study center for post-treatment visits at 30 (+3) days and at 90 (+7) days after the last dose of study drug. The following procedures will be performed at these visits:

- ECOG performance status evaluation
- Physical examination
- Weight and vital signs measurements
- Clinical chemistry, hematology, and urinalysis tests
- TSH, free T4, and free T3 tests

- Pregnancy test
- Tumor assessment (obtain tumor assessment by CT scan or MRI for patients who have not progressed at the time of study drug discontinuation [every 2 months (approximately  $60 \pm 7$  days) until the occurrence of progressive disease or study completion]; see details in Section 11.1.1) after every even cycle for the first 9 months of the study and after every third cycle thereafter
- Brain scan with contrast (obtain brain scans by MRI or CT for patients who have not progressed at the time of study drug discontinuation [may be performed within 4 weeks])
- [REDACTED]
- Plasma PK sample for measurement of atezolizumab concentration (30 [+3] and 90 [+7] days after the last dose of study drug)
- [REDACTED]
- Immunologic markers blood sample collection (90 [+7] days after the last dose of study drug, only)

AEs and concomitant medications will be collected through 30 days after the last dose of study drug; SAEs and AESI will be collected through 90 days after the last dose of study drug.

After completing the post-treatment visits, patients will enter the long-term Survival Follow-up Phase.

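### SAP Table 18 counts post-treatment laboratory windows from the first dose of the last cycle, so no on-schedule 90-day visit falls in a window and 30-day visits can be mislabelled; only descriptive by-visit summaries are affected.

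*SAP*

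**What the plan says.** Protocol Table 9-1, footnote c, sets the schedule: "Patients will return to the study center for post-treatment visits at 30 (+3) and 90 (+7) days after the last dose of study drug". Protocol 10.6 repeats it ("post-treatment visits at 30 (+3) days and at 90 (+7) days after the last dose of study drug"), and footnote c of SAP Table 2 agrees. None of the three allows an early visit.

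SAP Table 18 has two post-treatment columns, with identical limits for chemistry and hematology:

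- *Post-treatment*: "From first dose date of last cycle to first dose date of last cycle + 30".
- *Post-Treatment Visit + 60 days*: counted from the same date, "the last assessment falling the window between 31 and 89".

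No later window is defined. The text of SAP 6.1.3 adds that "Visit-based summaries will be based on the windowed visits" and, on which record to keep, "For the assigned follow-up visit, the last assessment in the window will be included in the summary". Footnotes d and e describe the two visits with other tolerances: "30 ± 3 days after the last dose of study drug" and "60 ± 7 days after the post-treatment visit".

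**The concern.** The windows and the visits are counted from different dates. The windows start at the first dose of the last cycle and the visits are timed from the last dose, which can be two days later. Even where the two dates coincide, the limits stop at or before the earliest permitted visit day: +30 is the first day of the 30-day visit, and 89 is one day short of the 90-day visit.

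Two things can then go wrong in the by-visit tables. The 90-day value belongs to no row. The 30-day value can land in the *+ 60 days* row, leaving the *Post-treatment* row to be filled from within the treatment cycle. These rows are where a reader would look for recovery of counts and late chemistry changes, during a period in which SAEs and AESIs are collected for 90 days after the last dose.

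**Working it through.** **Inputs**

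- Visit days after last dose: 30-33 (4 permitted days) and 90-97 (8 permitted days). Source: Protocol Table 9-1 and 10.6; SAP Table 2.
- Windows in days from first dose of the last cycle: 0 to 30 and 31 to 89. Source: SAP Table 18.
- Offset of last dose from first dose of the last cycle: 0 if the last dose is on Day 1 (any maintenance cycle; Protocol 8.4.4), and 2 if a full induction cycle is given, because trilaciclib or placebo and etoposide run to Day 3 (Protocol 8.1, 8.4.3.2). An offset of 1 covers a cycle stopped after Day 2.

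**Formula:** day from first dose = visit day after last dose + offset.

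| Last dose on | 30 (+3) visit | in 0-30 | in 31-89 | 90 (+7) visit | in 31-89 |
|---|---|---|---|---|---|
| Day 1 (+0) | 30-33 | 1/4 | 3/4 | 90-97 | 0/8 |
| Day 2 (+1) | 31-34 | 0/4 | 4/4 | 91-98 | 0/8 |
| Day 3 (+2) | 32-35 | 0/4 | 4/4 | 92-99 | 0/8 |

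**If 31-89 means study days** with Day 1 as the first dose, the offsets are 30 to 88 and the 90-day result is still 0 of 8.

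**Under footnotes d and e instead**

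- First visit at 30 ± 3 (days 27-33 after last dose): 3 of 7 permitted days fall in the second window after a Day 1 last dose, 4 of 7 after Day 2 and 5 of 7 after Day 3.
- Second visit 60 ± 7 days later: the earliest is 27 + 53 = 80 and the latest 33 + 67 = 100 (Day 1 last dose). Of the 7 × 15 = 105 combinations of permitted days, 49 fall by day 89; after a Day 3 last dose, 35 of 105 do.
- The nominal day is 30 + 60 = 90 after a Day 1 last dose and 92 after a Day 3 last dose, both outside.

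**What then fills the rows.** The first window opens on the first dose date and the last value in it is kept. If the 30-day visit falls on day 31 or later, the candidates for the *Post-treatment* row are:

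- Hematology, induction last cycle: the Day 22 sample (offset 21), or Day 15 if there is none.
- Chemistry, induction last cycle: the Day 1 sample, because Table 9-1 schedules chemistry on Day 1 only and Protocol 10.4 asks only for hematology and ECG on Day 22.
- Either panel, maintenance last cycle: the Day 1 sample.
- An unscheduled sample in any of these cases. The row is empty if there is none and the Day 1 sample was drawn before the first dose date.

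The *+ 60 days* row then shows the 30-day visit, or a later unscheduled sample up to day 89.

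**The case against.** **The windows may not apply after maintenance.** SAP 6.1.3 restricts windowing to induction cycles. That sentence concerns treatment cycles and gives maintenance cycles their nominal visits. Table 18 still has post-treatment columns, footnotes d and e refer to patients who have completed treatment, and the text has its own rule for follow-up visits. The wording could be clearer, but the post-treatment windows are defined.

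**Visit dates are unknown.** This stands in part. A reader might infer that most 30-day visits will be misplaced. The table counts permitted days, and the documents give no distribution of actual dates. After a maintenance last dose, a visit on exactly day 30 is placed correctly. Only the case of a Day 2 or Day 3 last dose is fixed, at 0 of 4. The 90-day result does not depend on dates within the permitted range.

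**The footnotes are looser.** Under their tolerances some second visits are caught, and after a Day 1 last dose 4 of 7 first-visit days are placed correctly. But those tolerances contradict Table 2 of the same SAP, and nominal day 90 is still outside.

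**The 90-day data are used elsewhere.** This stands and sets the size of the point. A reader might infer that the 90-day laboratory data drop out of the analysis. They do not:

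- SAP 6.2.8 summarizes continuous safety variables at end of study, using the last non-missing value.
- SAP 5.2.4 counts hepatic categories over all post-baseline assessments.
- SAP 6.2.8.3 takes worst-grade shifts from scheduled and unscheduled values.
- Listings show all data.

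One limit remains: the any-Grade-3/4 summary covers the overall treatment period, which ends with the last cycle (SAP 5), so it does not clearly recover 90-day values. None of these outputs shows recovery by visit.

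**In-cycle values under the label.** It would also go too far to say that the *Post-treatment* row generally holds a Day 15 or Day 22 value. That is possible only for hematology after an induction last cycle.

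**Conclusion.** The concern holds, as a minor point. Against the schedule in the protocol and SAP Table 2, no permitted day of the 90-day visit falls in any Table 18 window. For the 30-day visit, 3 of 4 permitted days after a Day 1 last dose, and all 4 after a Day 2 or Day 3 last dose, fall under the *+ 60 days* label. The *Post-treatment* row can then show an in-cycle value or be empty.

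This assumes that visits are held on schedule and that the last dose means the last dose of any study drug. The share of 30-day visits actually misplaced after maintenance cannot be stated from the documents.

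The effect is confined to descriptive by-visit laboratory summaries. Primary and key secondary endpoints are derived over the induction treatment period (SAP 5.1) without these windows. The counts-over-time displays in SAP 5.1.3.5 do use windowed visits, but they are supportive and descriptive, and by default cover the induction period (SAP 6.2.7). The documents therefore give no ground for inferring an effect on the efficacy conclusions.

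**What to change.** In SAP Table 18:

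1. Count both post-treatment windows from the last dose of any study drug, with limits that contain days 30-33 and 90-97. For example, 23-59 and 60-104 hold 4 of 4 and 8 of 8 permitted days. The Day 22 sample is then excluded: it is 22 - 3 = 19 days after a Day 3 last dose and 22 - 1 = 21 days after a Day 1 last dose. The outer limits are a choice; containing the permitted days is the requirement.
2. In each window, keep the value closest to day 30 or day 90 rather than the last one.
3. Align footnotes d and e with the 30 (+3) and 90 (+7) schedule.
4. State that a sample assigned to the post-treatment visit is not also used for the last induction cycle's EOC row. Without maintenance, EOC is Day 36 (SAP 5) and the hematology EOC window is Day 19 to EOC. After a Day 3 last dose the 30-day visit is on cycle Days 33-36, inside that window, and the example window of 23-59 corresponds to cycle Days 26-62. The chemistry EOC window, which opens on Day 2, overlaps in the same way.
5. Say explicitly that the post-treatment windows also apply to patients whose last cycle was maintenance.

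The cost is one table edit and a change to the windowing program. No data collection changes.
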